6.3.1.6 Follow-Up of Subjects Reporting Adverse Events

All AEs must be reported in detail on the appropriate page in the eCRF and be monitored to satisfactory resolution, until the investigator deems the event to be chronic or not clinically significant, or until the subject is considered to be stable.

6.3.2 Halting Rules

If in the opinion of the Investigator, the participation in the study is or is becoming detrimental to the well-being of a particular subject, this issue should be discussed with the medical monitor for this study and the subject's participation in the study may be discontinued.

Discontinuation of treatment should be considered if:

- ALT or AST > 8 × upper limit of normal (ULN)

- ALT or AST $> 5 \times$ ULN for more than 2 weeks
- ALT or AST $> 3 \times$ ULN and total bilirubin $> 2 \times$ ULN or international normalized ratio (INR) > 1.5
- ALT or AST $> 3 \times$ ULN with the appearance of fatigue, nausea, vomiting, right upper quadrant pain or tenderness, fever, rash, and/or eosinophilia (differential count $> 5\%$)

In the event that ALT or AST is $> 3 \times$ ULN, the subject will return for an unscheduled clinic visit and blood will be drawn for a coagulation panel to determine the INR. The INR will be determined at a local laboratory.

All subjects discontinued from the study should be followed until abnormal values return to normal, and all discontinuations should be discussed with the medical monitor prior to discontinuation.

6.3.3 Safety Assessments

The safety assessments will include AEs (Section 6.3.1), vital sign measurements, height and weight, concomitant medications, medical history, physical examination findings, transvaginal ultrasound, and clinical laboratory analyses (Section 6.6). Refer to Table 12–1 for a detailed schedule of the timing of study procedures.

6.3.3.1 Vital Sign Measurements

Vital sign measurements include oral temperature, seated BP, pulse rate, and respiration rate. Vital sign measurements will be collected as indicated in Table 12–1.

6.3.3.2 Height and Weight

Height will be measured at screening only and weight will be measured as indicated in Table 12–1.

6.3.3.3 Prior and Concomitant Medications

At the Screening Visit, the Investigator or designee must record the use of prescription and OTC medication taken within the prior 30 days. Concomitant medications (including

prescription and OTC medications) will be assessed and recorded throughout the study (Table 12–1).

6.3.3.4 Medical History

A detailed review of medical history, conducted at the Screening Visit, will include review of gravida, prior abortions, parity, deliveries, and history of gynecological conditions, surgeries, and cancer.

6.3.3.5 Physical Examination

The purpose of the physical examination is to identify any medical conditions that would impact eligibility of the subject at screening, and to identify any changes that occur as a result of treatment. Physical examination will include visual inspection, chest auscultation, organ and lymph node palpation, skin turgor, and brief neurologic exam (muscle strength, reflexes, sensation). The visual inspection should include a visual skin examination with specific attention to any androgenic changes (acne, hirsutism). Physical examinations will be performed as indicated in Table 12–1.

6.3.3.6 Transvaginal Ultrasound

Only for subjects with an intact uterus, transvaginal ultrasound will be performed at screening and at the end of treatment (Visit 5) to observe changes in the endometrial stripe thickness (mm). Transvaginal ultrasound examinations will be evaluated locally.

6.4 Other Assessments

6.4.1 Pelvic Examination

Gynecologic pelvic examination of each subject will be conducted at the Screening Visit and at Visit 5 (Table 12–1). The purpose of the pelvic examination at screening is to identify any gynecologic findings that might impact the patient's participation in the trial, and at the end of the treatment period to note whether any changes have occurred. The pelvic exam should include external inspection, speculum, and bimanual examinations.

6.4.2 Mammography

Mammography is the process of using low-energy x-rays to examine the human breast, which is used as a diagnostic and screening tool. The goal of mammography is the early

detection of breast cancer, typically through detection of characteristic masses and/or microcalcifications. Mammography examination of each subject will be conducted during the screening period unless the subject provides evidence of a mammography examination performed within the 6 months prior to screening (Table 12–1). Mammograms will be read locally.

6.4.3 Electrocardiography

A standard 12-lead ECG will be obtained at screening. Tracings must be dated and signed by the Investigator (or his/her designee) and filed with the subject's source documentation. Each ECG tracing should be labeled with the study number, subject initials (where regulations permit), and subject number. Interpretation of the tracing must be made by a qualified physician. Results from 12-lead ECG examination should be captured in the ECG Evaluation eCRF. Clinically significant abnormalities present at screening should be reported on the Medical History eCRF page. Clinically significant findings should be discussed with the medical monitor prior to randomizing the subject in the study. The PI will make the final decision if any observed deviations in the ECG are sufficient to require that the subject be excluded from the study. The ECG may be repeated at the discretion of the Investigator at any time during the study as clinically indicated, and any clinically relevant findings should be added to the AE eCRF.

6.5 Pregnancy

This study will enroll only postmenopausal women who are not taking hormone products. In the unlikely event of a pregnancy, any pregnancy must be reported to pharmacovigilance within 2 weeks of learning of its occurrence, using the EDC system (Section 6.3.1.3). The pregnancy must be followed-up to determine the outcome (including spontaneous miscarriage, elective termination, normal birth, or congenital abnormality) and status of mother and child, even if the subject was discontinued from the study. Pregnancy complications and elective terminations for medical reasons must be reported as an AE or SAE. Spontaneous miscarriages must be reported as an SAE.

Any SAE occurring in association with a pregnancy, brought to the investigator's attention after the subject has completed the study and considered by the investigator as possibly related to the study treatment, must be promptly reported to pharmacovigilance.

6.6 Laboratory Analyses

Any abnormal laboratory test results (hematology, clinical chemistry, or urinalysis) or other safety assessments (e.g., ECGs, radiological scans, or vital sign measurements), including those that worsen from baseline, felt to be clinically significant in the medical and scientific judgment of the investigator are to be recorded as AEs or SAEs.

However, any clinically significant safety assessments that are associated with the underlying disease, unless judged by the investigator to be more severe than expected for the subject's condition, are **not** to be reported as AEs or SAEs.

Laboratory analyses include the following:

- Comprehensive metabolic panel (Chem 14): includes calcium, carbon dioxide, glucose, potassium, sodium, total protein, and kidney and liver function tests (serum ALT, AST, γ -glutamyl transpeptidase, and total and direct bilirubin) will be performed (the investigator may repeat these checks if clinically indicated).
- Serum follicle stimulating hormone
- Complete blood count with differential
- Urinalysis dipstick testing for blood, protein, and leukocytes will be performed on a clean catch midstream voided urine specimen. If results or clinical symptoms indicate a possible urinary tract infection (UTI), the specimen will be sent for culture. If the culture is positive, the subject will receive appropriate treatment for UTI per standard of care. If the subject has a positive urine culture at the time of screening, she will be considered a screening failure and will not be enrolled until she has been treated for a UTI, the UTI symptoms disappear, and a dipstick urinalysis is consistent with the absence of a UTI. The subject will then be eligible for rescreening 1 additional time at the discretion of the Sponsor. After a subject has qualified for enrollment based on a negative urinalysis and the absence of clinical symptoms of a UTI, any subsequent UTI will be treated and the subject will continue in the study.
- Fasting lipid panel: including total cholesterol, low-density lipoprotein (LDL), high density lipoprotein (HDL), triglycerides, and HDL particle composition
- C-reactive protein (CRP)

- Serology for evidence of active infection with hepatitis B or hepatitis C
- Hormone panel: includes testosterone, free testosterone, and estradiol.
- SHBG

6.7 Sample Collections

Instructions for sample collection, handling, and shipping will be presented in a separate laboratory manual that will be provided to study sites as a separate document. Required blood samples should be 12-hour fasting samples.

7 Statistical and Analytical Plan

7.1 Primary Efficacy Endpoint

The primary efficacy endpoint is a responder analysis, where a responder is defined as having a $\geq 50\%$ reduction at the end of treatment (Week 12) compared to baseline in the mean number of stress incontinence episodes per day as assessed by the 3-day voiding diary. Subjects who have missing diary data for the Week 12 visit will be counted as non-responders for this analysis. Rules for recording valid diary data are presented in Section 6.2.1.

7.2 Secondary Efficacy Endpoints

The secondary efficacy endpoints in this study are the following assessments compared to baseline at each visit during the treatment period:

- Responder rate, where a responder is defined as having a $\geq 50\%$ reduction compared to baseline in the mean number of stress incontinence episodes per day as assessed by the 3-day voiding diary
- Change in the number of stress incontinence episodes per day as measured by the 3-day voiding diary
- Change in the total number of voids per day as measured by the 3-day voiding diary
- Change in the mean number of stress incontinence episodes per day as measured by the 3-day voiding diary
- Change in 24-hour pad weight as measured by the 24-hour pad weight test
- Change in the results of the Bladder Stress Test (BST)
- Change in subject-reported impression of SUI severity as measured by the PGI-S
- Change in subject-reported impression of SUI improvement as measured by the PGI-I
- Change in subject-reported urogenital distress as measured by the UDI-6
- Change in subject-reported impact of urinary incontinence on daily life as measured by the IIQ-7 Short Form

- Change in subject-reported impact of urinary incontinence on daily life as measured by the I-QOL
- Change in subject-reported sexual function as measured by the FSFI
- Change in subject-reported assessment of fecal incontinence as measured by the Vaizey Incontinence Severity Score.
- Change in subject-reported stress incontinence, urge incontinence, and mixed incontinence as measured by the MESA incontinence questionnaire (Week 12 only)

7.3 Exploratory Efficacy Endpoints

The exploratory efficacy endpoints in this study are the following assessments compared to Week 12 for all treatments at Week 16, Week 20, and Week 28:

- Responder rate, where a responder is defined as having a $\geq 50\%$ reduction compared to baseline in the mean number of stress incontinence episodes per day as assessed by the 3-day voiding diary
- Number of stress incontinence episodes per day as measured by the 3-day voiding diary
- Total number of voids per day as measured by the 3-day voiding diary
- Change in 24-hour pad weight as measured by the 24-hour pad weight test
- Subject-reported impression of SUI severity as measured by the PGI-S
- Subject-reported impression of SUI improvement as measured by the PGI-I
- Subject-reported urogenital distress as measured by the UDI-6
- Subject-reported impact of urinary incontinence on daily life as measured by the IIQ-7 Short Form
- Subject-reported impact of urinary incontinence on daily life as measured by the I-QOL
- Subject-reported sexual function as measured by the FSFI
- Subject-reported assessment of fecal incontinence as measured by the Vaizey Incontinence Severity Score

Additional sensitivity analyses may be included in exploratory analyses. These analyses will be described in further detail in the SAP.

7.4 Sample Size Calculation

The sample size calculation was performed using PASS v12.0.1 for binary outcomes. The sample size calculation was performed for a binary response (i.e., a responder is defined as having a $\geq 50\%$ reduction at the end of treatment compared to baseline in the mean number of stress incontinence episodes per day as assessed by the 3-day voiding diary). The assumptions were a 60% active treatment response and 40% placebo response. The overall discontinuation rate was anticipated to be approximately 25%.

Given these assumptions, a randomized sample size of approximately 400 subjects (randomized in a 1:1:1 ratio for placebo, 1 mg GTx-024, and 3 mg GTx-024, respectively) will have 80% power to detect a treatment difference of 20%. A 2-sided hypothesis test with 5% significance is assumed for each pairwise comparison between GTx-024 and placebo (i.e., alternatively using a 1-sided significance level of 2.5%).

7.5 Analysis Sets

Data analysis will be performed on a full analysis set (FAS), a per protocol set (PPS), an intent-to-treat (ITT) set, a durability set (DS), and a safety analysis (SA) set.

The FAS is used for the primary analysis. The FAS consists of all randomized subjects who receive at least 1 dose of study drug and have at least 1 post baseline primary efficacy assessment (3-day voiding diary). All analyses using the FAS will group participants according to randomized treatment.

The PPS is used for a supportive analysis and will be defined as all subjects included in the FAS who do not have any significant protocol deviations. All analyses using the PPS will group subjects according to treatment actually received.

The ITT set consists of all randomized subjects who receive at least 1 dose of study drug. All analyses using the ITT set will group subjects according to randomized treatment. Subjects who do not have any postbaseline assessments will be treated as non-responders for ITT analyses.

The DS is used for exploratory analyses to assess the durability of the effect of treatment and will be defined as all subjects who complete a Week 12 final visit and a Week 16, Week 20, or Week 28 assessment.

The SA set contains all subjects randomized in the study who receive at least 1 dose of study drug. All analyses using the SA set will group subjects according to treatment actually received.

All efficacy analyses performed on the FAS will be repeated on the PPS and the ITT set. Further details will be provided in the SAP.

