Given these assumptions, a randomized sample size of approximately 400 subjects (randomized in a 1:1:1 ratio for placebo, 1 mg GTx-024, 3 mg GTx-024, respectively) will have 80% power to detect a treatment difference of 20%. A 2-sided hypothesis test with 5% significance is used for each pairwise comparison between GTx-024 and placebo (i.e., alternatively using a 1-sided significance level of 2.5%).

Analysis Sets:
	
Data analysis will be performed on a full analysis set (FAS), a per protocol set (PPS), an intent-to-treat (ITT) set, a durability set (DS), and a safety analysis (SA) set.
 
The FAS is used for the primary analysis. The FAS consists of all randomized subjects who receive at least 1 dose of study drug and have at least 1 post baseline primary efficacy assessment (3-day voiding diary). All analyses using the FAS will group participants according to randomized treatment.
 
The PPS is used for a supportive analysis and will also be defined as all subjects included in the FAS who do not have any significant protocol deviations. All analyses using the PPS will group subjects according to treatment actually received.
 
The ITT set consists of all randomized subjects who receive at least 1 dose of study drug. All analyses using the ITT set will group subjects according to randomized treatment. Subjects who do not have any postbaseline assessments will be treated as non-responders for ITT analyses.
 
The DS is used for exploratory analyses to assess the durability of the effect of treatment and will be defined as the first 225 randomized subjects who complete a Week 12 final visit and at least one assessment during the Durability period.
 
The SA set contains all subjects randomized in the study who receive at least 1 dose of study drug.
 
All efficacy analyses performed on the FAS will be repeated on the PPS and the ITT set.

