2.1 Primary Objective

The primary efficacy objective of this study is to compare the efficacy of GTx-024 (1 mg and 3 mg administered once daily) to that of placebo by evaluating the mean number of subject-reported stress incontinence episodes per day through a responder analysis, where a responder is defined as having a $\geq 50\%$ reduction at the end of treatment (Week 12) compared to baseline in the mean number of stress incontinence episodes per day as assessed by the 3-day voiding diary. Subjects who have missing diary data for the Week 12 visit will be counted as non-responders for this analysis.

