6.1.3 Study Visit 2: Week 1, Phone Visit

Approximately 1 week after beginning treatment, the subject will be contacted by phone to assess for concomitant medications and AEs (which will be recorded in the eCRF). The subject will be instructed to complete a 24-hour pad weight and 3-day voiding diary within the week preceding her next study visit. The subject will be reminded to bring all unused study drug (in its original packaging) to her next clinic visit.

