6.1.4 Study Visit 3: Week 4, Clinic Visit

Approximately 4 weeks after beginning treatment, the subject will return to the study site for a clinic visit. Unused study drug will be collected. Concomitant medications and AEs will be reviewed. Weight and vital signs will be measured, and a physical examination will be performed. A dipstick urinalysis will be performed, and blood will be drawn for a comprehensive metabolic panel (CMP). Completion of a 24-hour pad weight test and a 3-day voiding diary will be verified.

The subject will complete the UDI-6, IIQ-7 Short Form, I-QOL, FSFI, PGI-S, PGI-I, and Vaizey Incontinence Severity questionnaires.

Study drug will be dispensed with administration instructions, and each package will be preprinted with a medication identification number. The medication identification number assigned to the subject will be noted in the eCRF for study drug.

The subject will be instructed to complete a 24-hour pad weight and 3-day voiding diary within the week preceding her next study visit. The subject will be reminded to bring all unused study drug (in its original packaging) to her next clinic visit.

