7.7.1 Analysis of the Primary Efficacy Endpoint

The primary analysis will be conducted on the primary endpoint using the FAS.

The primary efficacy endpoint (i.e., a binary response indicator where a responder is defined as having a $\geq 50\%$ reduction at the end of treatment compared to baseline in the mean number of stress incontinence episodes per day as assessed by the 3-day voiding diary) will be evaluated using a logistic regression model. The logistic regression model will include treatment group as a covariate. The odds ratio of response between each dose level of GTx-024 and placebo (together with the corresponding 95% confidence interval) will be reported. The null hypothesis is that there is no treatment effect for either dose level of GTx-024. This will be tested against the alternative hypothesis that there is a treatment effect for at least 1 of the dose levels of GTx-024.

The corresponding *P*-value for the comparison between each dose level of GTx-024 and placebo will be derived using the standard normal distribution. Subjects who have missing diary data for the screening period or the Week 12 visit will be counted as non-responders for this analysis.

Sensitivity analyses will be specified in the SAP.

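### The primary analysis set drops dosed women who give no post-baseline diary, while every other missing Week 12 diary counts as non-response; making the already planned ITT set primary would cure this cheaply.

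*Combined protocol and SAP*

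**What the plan says.** Section 7.5 and the synopsis both state: "The FAS is used for the primary analysis". Section 7.7.1 repeats it: "The primary analysis will be conducted on the primary endpoint using the FAS". To enter the FAS a randomized woman must have taken a dose and "have at least 1 post baseline primary efficacy assessment (3-day voiding diary".

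The rule for missing data is written into the primary objective (Section 2.1) with no restriction to the FAS: "Subjects who have missing diary data for the Week 12 visit will be counted as non-responders for this analysis". Section 7.1 has the same rule, and Section 7.7.1 extends it to a missing screening diary.

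The ITT set in Section 7.5 is all randomized women who took a dose, grouped as randomized. For it the plan says: "Subjects who do not have any postbaseline assessments will be treated as non-responders for ITT analyses". It is already scheduled: "All efficacy analyses performed on the FAS will be repeated on the PPS and the ITT set".

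The first post-baseline diary belongs to Week 4. At the Week 1 call the woman is told to complete a "3-day voiding diary within the week preceding her next study visit", and Section 6.1.4 has it checked at that visit: "Completion of a 24-hour pad weight test and a 3-day voiding diary will be verified".

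**The concern.** Whether a woman gives any post-baseline diary is settled after randomization and could depend on treatment. One who gives a Week 4 diary and then leaves is a failure in the primary analysis. One who leaves earlier and gives no diary is removed from it. Neither has a Week 12 diary, and the plan gives no reason for the difference.

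If the target is response among all dosed women, as the non-response rule suggests, the FAS comparison is biased whenever this early loss differs between arms. The bias can favour the drug or placebo. The ITT repeat would show a discrepancy, but the FAS result would still govern the primary conclusion.

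**Working it through.** **Inputs from the plan (Section 7.4).** Response 60% on active and 40% on placebo, about 25% overall discontinuation, about 400 women randomized 1:1:1 (133 per arm), two-sided 5% per comparison, 80% power.

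**Reproducing the plan's figure.** The pooled-variance formula without continuity correction needs 97 per arm. Then 97 / (1 − 0.25) = 130 per arm after rounding up, and 3 × 130 = 390, against about 400 stated. With 133 × 0.75 ≈ 100 evaluable per arm, power is 81%. So 60% and 40% read naturally as rates among completers. With discontinued women counted as failures they become 0.75 × 60% = 45% and 0.75 × 40% = 30%.

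**How many women could be affected.** The documents do not say. If the 25% were spread evenly over 12 weeks (assumed), the loss by Day 21 would be 25% × 21/84 = 6.25%, or 8.3 women per arm. Any who give a usable diary on withdrawal would not be excluded.

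**Bias and error of the FAS when the arms are truly equal.** Let the true response among all dosed women be 30% in both arms. An arm with early loss x then has FAS response 0.30 / (1 − x). At 10% loss on drug and 5% on placebo: 0.30/0.90 − 0.30/0.95 = 33.3% − 31.6% = 1.8 points. Error rates come from 1,000,000 simulated trials per setting, with a Wald test of the log odds ratio at |z| > 1.96:

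| Early loss, drug / placebo (assumed) | False FAS difference | FAS error favouring drug | FAS two-sided error |
|---|---|---|---|
| 5% / 5% | 0 | 2.5% | 4.9% |
| 7.5% / 5% | +0.9 points | 3.4% | 5.2% |
| 10% / 5% | +1.8 points | 4.7% | 5.9% |
| 5% / 7.5% | −0.9 points | 1.7% | 5.2% |
| 5% / 10% | −1.8 points | 1.2% | 5.9% |

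The ITT analysis stays at 2.5% favouring drug and 4.9% to 5.0% two-sided in every row.

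**The opposite null.** Suppose instead that response is equal (33.3%) among women who stay. The FAS then holds 4.9% to 5.0%, and the ITT difference is off by 0.8 points at 7.5%/5% and 1.7 points at 10%/5%, with two-sided error of 5.2% and 6.0%.

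**Fixed-data examples.** 133 per arm; z = ln(OR) / √(1/a + 1/b + 1/c + 1/d), where a to d are the four cell counts.

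| Responders, drug vs placebo | Left out of FAS, drug / placebo | ITT p | FAS p |
|---|---|---|---|
| 55 vs 40 | 10 / 7 | 0.056 | 0.036 |
| 56 vs 40 | 7 / 10 | 0.042 | 0.054 |
| 55 vs 40 | 8 / 8 | 0.056 | 0.051 |

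For the first row, ITT has ln(OR) = 0.494, SE = 0.258, z = 1.91. The FAS (55/123 vs 40/126) has 0.553, 0.264, z = 2.10. In the first two rows an imbalance of three women changes the verdict. In the balanced third row nothing changes.

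**Power cost of ITT (simulated, equal early loss in both arms).**

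| Early loss per arm (assumed) | FAS at 45% vs 30% | FAS at 60% vs 40% |
|---|---|---|
| 2% | 72.3% | 91.4% |
| 5% | 73.1% | 92.1% |
| 10% | 74.7% | 93.7% |
| ITT, any of these | about 71.8% | about 90.3% |

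The last column applies if 60% and 40% already count missing diaries as failures.

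**Minor secondary point: baseline covariate.** The primary logistic model has treatment only, whereas the MMRM in Section 7.7.2 adjusts for baseline. In 10,000 simulated trials per setting, adding baseline moved power from 71.3% to 70.9% at an assumed odds ratio of 1.0 per SD, from 71.0% to 73.1% at 1.65, and from 71.6% to 76.2% at 2.2.

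**The case against.** The strongest reply is that nothing is hidden. The ITT analysis is prespecified, counts these women as failures and repeats every FAS efficacy analysis. Sensitivity analyses are left to a separate SAP, which is not in the text reviewed here. True, but a supportive repeat does not settle which result governs.

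Second, the bias depends on the target chosen: under equal response among women who stay, the FAS is right and ITT is wrong by about as much. That stands as arithmetic. The plan does not adopt that target, however. It counts later leavers as failures, and Section 4.2.2 commits to using data from all subjects, early withdrawals included.

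Third, the effect is small and needs an imbalance that the documents do not predict. This stands, and it limits the weight of the point. The two reversing examples were placed at the significance limit. With 57 vs 40 responders and 7/10 left out, both analyses are significant (ITT 0.031, FAS 0.040).

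Fourth, the size of the excluded group is uncertain. End-of-treatment measures are sought at early withdrawal (Sections 4.2.2 and 6.1.6), which would shrink it. But Section 6.2.1 accepts a diary only within 7 days of a planned visit, and the plan does not say whether an off-window withdrawal diary qualifies a woman for the FAS, which could enlarge it.

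Fifth, the treatment-only primary model matches the plan's own approach to binary secondary endpoints. That is so, and the covariate remains only a minor suggestion.

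**Conclusion.** The concern holds as a worthwhile improvement, not as a demonstrated error. The plan treats women with the same missing outcome differently because of an event after randomization, and it already contains the analysis that avoids this.

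For a target of response among all dosed women, the FAS has no type I error inflation under equal early loss. Under assumed losses of 10% against 5% it is off by 1.8 points in either direction, with two-sided error of 5.9% and error favouring the drug between 1.2% and 4.7%. All early-loss rates are assumptions; the documents give only the 25% overall figure. The practical risk lies in a result close to p = 0.05.

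**What to change.** Before unblinding, change the synopsis, Sections 7.5 and 7.7.1 and the SAP to read:

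> The primary analysis uses the ITT set (all randomized subjects who receive at least 1 dose, as randomized; missing Week 12 diary = non-responder). The FAS and PPS are supportive.

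Stating the rule in terms of the Week 12 diary also covers a woman who has post-baseline questionnaires but no diary.

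**Cost.** No new patients, data or analyses are needed, but the protocol text changes, and under Section 10.2.1 that requires sponsor and IRB approval. Reported response rates fall slightly. Power falls by about 0.4, 1.3 or 2.9 points if 2%, 5% or 10% of each arm give no post-baseline diary, or by 1.1 to 3.3 points if 60% and 40% already count missing diaries as failures. Most of the gap between the planned 80% and about 72% comes from the non-response rule, which the FAS analysis already applies.

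**Minor addition.** Add baseline mean stress episodes per day to the primary logistic model. Keep any woman with a missing screening diary as a non-responder with an imputed baseline value, for example the overall mean. This costs one model term and a rule that should rarely be used, because eligibility requires a screening diary (Section 4.1.1). The gain is about 0 to 5 power points for assumed odds ratios of 1.0 to 2.2 per SD.

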7.7.3 Analysis of Exploratory Efficacy Endpoints

Durability of treatment effect will be examined in the DS for the exploratory efficacy endpoints. Additional sensitivity analyses of exploratory and secondary efficacy endpoints may also be conducted as exploratory analyses, including sensitivity analyses with regard to missing data. Further details of the exploratory analyses will be provided in the SAP.

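### Durability responder rates may be overstated: the durability set requires completing Week 12 and returning off drug, and the missing-diary rule is not extended past Week 12.

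*Combined protocol and SAP*

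**What the plan says.** - **Durability set.** Section 7.5 includes "all subjects who complete a Week 12 final visit and a Week 16, Week 20, or Week 28 assessment". The synopsis (Analysis Sets) limits the set to the first 225 randomized "who complete a Week 12 final visit and at least one assessment during the Durability period". Section 3.1 gives Week 20 and 28 visits only to the first 225; everyone else ends at Week 16.
- **Use of the set.** Section 7.7.3: "Durability of treatment effect will be examined in the DS for the exploratory efficacy endpoints". Section 7.3 lists the responder rate at Weeks 16, 20 and 28 and compares these visits with Week 12.
- **Missing diaries.** Section 7.1: "Subjects who have missing diary data for the Week 12 visit will be counted as non-responders for this analysis". Section 7.7.1 adds a missing screening diary. The ITT rule in Section 7.5 covers women with no post-baseline assessment, and the ITT repeat applies to full-analysis-set analyses, not to durability-set analyses.
- **Early stoppers.** Under Section 4.2.2 a woman who stops treatment is treated as having left the study, so early stoppers largely fall outside the durability set.
- **Deferred detail.** Section 7.7.3 makes missing-data sensitivity analyses for these endpoints optional. It leaves further detail to a separate SAP, which Section 7.7 promises before unblinding and which is not in the supplied text.

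**The concern.** Membership of the durability set depends on two things that happen after randomization: finishing Week 12, and having at least one off-drug assessment. One off-drug assessment is enough to qualify. A woman can therefore attend Week 16, relapse, stop attending, and be absent from the Week 20 and 28 denominators. No stated rule scores her as a non-responder.

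Two consequences follow. First, attendance can move the durability rate, and relapse, which the analysis is meant to detect, is a plausible reason for not attending. Second, a durability rate set beside the primary Week 12 rate has a different denominator and a different missing-data rule. The arms within the set are also no longer protected by randomization if reasons for leaving differ between them.

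**Working it through.** **The plan's own figure.** Section 7.4 says: "The assumptions were a 60% active treatment response and 40% placebo response". It assumes about 25% discontinuation, 80% power and a 2-sided 5% test.

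- Per arm: (1.96 × √(2 × 0.5 × 0.5) + 0.842 × √(0.24 + 0.24))² / 0.20² = 96.9, so 97 evaluable.
- Inflated: 97 / 0.75 = 129.3, so 130 per arm and 390 in three arms. This agrees with "a randomized sample size of approximately 400 subjects".
- Check: 400 / 3 × 0.75 = 100 evaluable per arm gives 81.2% power.

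The figure reproduces only if 60% and 40% apply to evaluable women and dropout is added afterwards. The illustration below therefore takes 60% as the response among completers.

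**Size of the cohort.** 225 / 3 = 75 per arm, and 75 × 0.75 = 56.25 complete Week 12. Week 12 responders on active drug: 0.60 × 56.25 = 33.75.

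**Week 28 illustration.** Assumed: one third of responders relapse (11.25, leaving 22.5), half of the relapsers are absent (5.625), and everyone else attends. The plan states no rule for absent women, so the durability set is taken as observed cases.

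| Active arm | Week 12 | Week 28, all attend | Week 28, half of relapsers absent |
|---|---|---|---|
| Durability set, observed | 33.75/56.25 = 60% | 22.5/56.25 = 40% | 22.5/50.625 = 44.4% |
| All 75, missing = non-response | 33.75/75 = 45% | 22.5/75 = 30% | 22.5/75 = 30% |

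The overstatement is 44.4 − 40 = 4.4 points. If the absent relapsers attended Week 16, they stay in the set at Week 12, and the fall shown is 60 − 44.4 = 15.6 points instead of 20.

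The same assumptions on placebo: 0.40 × 56.25 = 22.5 responders, 15 still responding, 3.75 absent. Observed 15/52.5 = 28.6%, true 15/56.25 = 26.7%. The difference between arms is 15.9 points observed against 13.3 true.

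**Dependence on who leaves.** Assumed: 80% of Week 12 responders keep their response, so the true active rate among completers is 0.60 × 0.80 = 48%. With off-drug loss a in responders and b in non-responders, the observed rate is 0.48(1 − a) / [0.48(1 − a) + 0.52(1 − b)].

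| Loss: responders / non-responders | Observed | Bias against 48% |
|---|---|---|
| 10% / 10% | 48.0% | 0 |
| 5% / 20% | 52.3% | +4.3 |
| 10% / 30% | 54.3% | +6.3 |
| 20% / 10% | 45.1% | −2.9 |

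**Difference of scale.** For the same observed responders, dividing by attenders can never give less than dividing by everyone. At 25% discontinuation and no later loss, the factor is 1 / 0.75 = 1.33: 60% becomes 45% on active drug, 40% becomes 30% on placebo, and the difference falls from 20 to 15 points. Against the primary analysis this factor is an upper limit, because the full analysis set also leaves out women with no post-baseline diary.

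**The two definitions.** With 25% discontinuation and no later loss, Section 7.5 admits 400 × 0.75 = 300 women and the synopsis 225 × 0.75 = 169. The other 131 have no Week 20 or 28 visit by design. Counting them as failures would turn 22.5/56.25 = 40% into 22.5/100 = 22.5% per active arm.

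**The case against.** - **Direction.** No off-drug loss by response status is given. Women who complete the study may be offered an open-label extension with study drug (Section 3.1), which gives relapsing women a reason to keep attending. This stands: the bias could be positive, zero or negative.
- **A stronger reading.** A reader might infer that the durability rates are certainly inflated and that relapse would be hidden. If 60% held on the randomized denominator, the set would show 45/56.25 = 80% at Week 12. After one-third relapse with half of the relapsers absent, Week 28 would be 30/48.75 = 62%, which looks like full maintenance of 60%. The documents do not support this. The sample-size arithmetic places 60% among completers. Section 7.3 compares durability with Week 12, and within the set even these numbers fall visibly, from 80% to 62%. The illusion needs a cross-set comparison that the plan does not specify.
- **A legitimate question.** Durability among women who finished treatment is worth asking, and the set answers it if labelled so. This stands, and it argues against replacing the completer analysis. A Week 12 anchor in the same women removes the mismatch at Week 12 but does not deal with later loss.
- **Deferred detail.** The SAP may contain a rule. It cannot be said that the final plan has none, only that the supplied text states none.
- **Differential loss.** Section 3.1.1.1 reports ALT adverse events in 20.8% at 3 mg and 0% on placebo in an earlier study, with one discontinuation at 3 mg. That makes arm-dependent loss possible; it does not show it.

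**Conclusion.** The concern holds in a limited form. Both definitions condition on events after randomization, and the supplied text gives no rule for a missing Week 16, 20 or 28 diary. Durability responder rates may therefore be overstated if relapsing women stop attending. The size is about 4 points with 60% response among completers, one third of responders relapsing and half of the relapsers absent, and about 4 to 6 points in the other scenarios where non-responders leave more often. It is zero with equal loss and about −3 points when responders leave more often. All relapse and off-drug loss figures are assumptions.

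Two parts do not depend on those assumptions: durability and primary rates are on different denominators and missing-data rules, and the two set definitions conflict. Durability is exploratory and no between-arm durability test is specified in the supplied text, so the primary conclusion is not affected.

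**What to change.** 1. Reconcile Section 7.5 with the synopsis first, so that women with no planned Week 20 or 28 visit are not scored as failures. State also whether an early-withdrawal Visit 5 counts as completing Week 12, since the schedule of events uses one column for both.
2. State the missing-diary rule for Weeks 16, 20 and 28 in the SAP.
3. Beside the durability-set analysis, report Week 12, 16, 20 and 28 responder rates for all dosed women among the first 225 randomized, by randomized arm, with a missing diary counted as non-response.
4. For each set, show the Week 12 rate in the same women as the anchor.
5. Label the durability-set result as durability among treatment completers who returned.

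The cost is some wording and one extra table. The downside is that women lost for administrative reasons count against durability in the added analysis, which is why it belongs beside the durability-set result and does not replace it.
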